## PRÉCIS

Prevention of oral chronic graft versus host disease (GVHD) by topical agents is an attractive strategy because it would potentially avoid the adverse effects associated with systemic immunosuppression. Topically administered dexamethasone solution is a commonly used agent for the prophylaxis of oral inflammatory conditions including GVHD. However, the efficacy and systemic effects of topically administered dexamethasone solution are unknown. We therefore propose this trial designed to evaluate the efficacy and safety of topical dexamethasone solution for prevention of oral chronic GVHD in stem cell transplant recipients.

This pilot phase II study will follow a randomized, double-blind, placebo controlled, parallel group design. Consenting subjects who have undergone hematopoietic stem cell transplantation at the NIH Clinical Center and the surrounding transplant clinics will be randomized 50/50 to receive dexamethasone 0.01% solution or placebo as an oral rinse for 3 months starting 90-100 days post-transplant. Subjects will be evaluated monthly after the start of intervention. Diagnostic and research evaluations will include a complete oral examination, oral mucosal biopsy prior to the beginning of the intervention (day -7) and at the time of development of oral chronic GVHD or at the completion of intervention in the absence of clinical GVHD. We will measure serum dexamethasone levels and perform short cosyntropin (ACTH stimulation) test at the end of the 3 months of intervention or onset of clinically significant GVHD.

The primary objective of the study is to evaluate the safety and efficacy of topical dexamethasone 0.01% solution used as an oral rinse for prevention of oral chronic GVHD. Our primary endpoint will be the proportion of subjects that develop clinically significant (severity score 3 or higher) oral chronic GVHD after three months.

Secondary objectives will include the impact of oral chronic GVHD on the quality of life, characterization of the changes in tissue and salivary biomarkers associated with development of oral graft versus host disease, and measures of the effects of topical dexamethasone on hypothalamo-pituitary-adrenal axis. Secondary outcomes will include oral cavity specific quality of life as measured by OHIP-14 questionnaire, oral discomfort levels, improvement in general quality of life scores, and severity of oral chronic GVHD as measured by the site-specific GVHD scoring system.

---

 The term prophylaxis, preventive treatment and treatment are used interchangeably. Treatment using oral dexamethasone will always mean prophylactic treatment.

# 1. OBJECTIVES

## 1.1 Primary Objective

To evaluate the safety and efficacy of topical dexamethasone 0.01% solution used as an oral rinse for prevention of oral chronic graft versus host disease (GVHD).

## 1.2 Secondary Objectives

- 1.2.1 To assess the incidence, risk factors and clinical characteristics of oral chronic GVHD.
- 1.2.2 To evaluate the impact of oral chronic GVHD on quality of life.
- 1.2.3 To evaluate the degree of systemic absorption of topical dexamethasone and its effect on adrenal cortical function.
- 1.2.4 To evaluate changes in salivary and plasma proteome associated with oral chronic GVHD.
- 1.2.5 To evaluate tissue kinetics and gene expression patterns of immune cells associated with the development of chronic oral GVHD and prophylaxis with topical dexamethasone.
- 1.2.6 To assess the predictive value of subclinical tissue changes on development of chronic oral and systemic GVHD and prognostic significance of these changes in terms of graft versus tumor effect.

# 2. BACKGROUND

## 2.1 Graft Versus Host Disease

In recent years, allogeneic stem cell transplantation has been used increasingly for malignant disorders, including solid tumors [1, 2]. GVHD is a major complication and a leading cause of morbidity and mortality in recipients of allogeneic stem cell transplantation. GVHD results from immunologic attack by the donor immune cells on the tissues and organs of the recipient. Skin, gastrointestinal tract, and liver are the most commonly targeted organs. The incidence and severity of GVHD can vary depending on the degree of mismatch of major histocompatibility antigens of the donor and host, age of donor and recipient, source of stem cells, and the type of the preparative regimen. With development of non-myeloablative conditioning regimens, the early post-transplant mortality has dropped with more patients developing GVHD. Given the undersupply of related donors, the use of unrelated and partially matched unrelated donors is likely to expand. As our population ages, the use of both older donors and recipients will become more frequent [3]. These factors are likely to increase the incidence of GVHD in the coming years.

Traditionally, GVHD was classified arbitrarily as acute (occurring within 100 days of transplant) and chronic (occurring 100 days or more after transplant) [4]. Overall, up to seventy percent of patients who survive more than 100 days after transplantation will develop the chronic form of GVHD with the majority manifesting in the first year [5-8]. Chronic GVHD has many features of known autoimmune diseases, such as lupus, lichen planus, and scleroderma, and can have a varied clinical presentation. Mononuclear cellular infiltrates can be found in many areas of the graft recipient, including the liver, skin, oral mucosa, and salivary glands.

In order to provide prognostic and treatment guidelines, chronic GVHD has been classified as limited and extensive depending on the number of the organs involved and the severity of the disease [3]. Limited chronic GVHD was defined as isolated skin involvement less than 50% with or without liver dysfunction and did not require systemic immunosuppression. In contrast, extensive chronic GVHD had evidence of skin, mouth, eyes, liver or other target organ involvement. A more recent classification based on several

risk factors appears to better stratify this complex patient population [9]. This complication of transplant can persist for months to years, and requires long-term management by multiple disciplines.

## 2.2 Oral Involvement in Chronic GVHD

Oral chronic GVHD is common and is a major cause of morbidity and loss of quality of life in long-term survivors[10, 11]. In a recent randomized trial of peripheral blood stem cell (PBSC) vs. bone marrow stem cells (BMSC) transplants, oral mucosal changes were the most common manifestation of chronic GVHD in BMSC recipients and the second most common (after skin) in PBSC transplants. Overall incidence was around 85% [5]. Oral manifestations of the chronic GVHD include lichenoid changes, mucosal atrophy and ulcerations, taste disturbances, and salivary gland hypofunction. Oral pain and food sensitivity are common and not limited to patients with ulcerations [12, 13]. Oral discomfort was shown to be associated with decrease in food intake and weight loss in this group of subjects [14]. No studies have evaluated the impact of oral chronic GVHD on quality of life after stem cell transplantation.

There have been several reports of increased incidence of oral squamous cell carcinoma (SCCA) after hematopoietic stem cell transplantation (HSCT) [15, 16]. Oral chronic GVHD was an independent risk factor for SCCA after HSCT. Most of the cases described occurred in patients treated with myeloablative conditioning. It is unknown whether early or preventive treatment of oral chronic GVHD can decrease incidence of subsequent SCCA.

The incidence of chronic GVHD in the placebo group was originally estimated as 0.6 based on the published literature. The reported incidence varies from 38 to 83% depending on the type of stem cell transplantation (as shown in the table below). Peripheral blood stem cell (PBSC) transplantation had a higher incidence of chronic oral GVHD compared to bone marrow transplantation. At our institute, we use peripheral blood stem cell as a stem cell source. However there are different protocols utilizing T-cell depleted peripheral stem cell transplantation which provides similar T cell dose (10-H-0154) or even a smaller T cell (06-H-0248, 12-H-0028) dose as the ones used in bone marrow grafts. Furthermore, most literature reported the incidence of chronic oral GVHD irrespective of its severity. Busca et al. (Haematologica 2005; 90: 567) reported up to 62.5% of chronic oral GVHD were graded as moderate to severe (equivalent to grade 3 or higher). Therefore, the incidence of clinically significant (grade 3 or higher) oral chronic GVHD at day 90 after randomization, a primary endpoint of this study would be potentially around 40%, much lower than 60%.

Author	Journal	N	Study population	Incidence of chronic oral GVHD
Flowers	Blood 2002; 100: 415	95	Adult bone marrow or PBSC	Bone marrow 70% PBSC 83%
Busca	Haematologica 2005; 90: 567	104	Adult bone marrow	All grade oral GVHD 38% (62.5% had moderate to severe chronic oral GVHD)
Treistner	Biol Blood Marrow Transplant 2005; 11: 721	49	Pediatric bone marrow	45%
Pavletic	Am J Hematol 2005; 78: 265	87	Adult bone marrow or PBSC	Bone marrow 53% PBSC 70%

## 2.3 GVHD Prophylaxis

07-H-0005

[name].

February 3, 2021

Amendment AA

Currently, all subjects undergoing stem cell transplantation receive some form of acute GVHD prophylaxis with systemic immunosuppressive agents, most commonly cyclosporine with methotrexate. The duration of this regimen is based on past studies where the majority of severe GVHD occurred in the first 100 days post transplant. Therefore, subjects typically are maintained on immunosuppression for the first 100 days which in the absence of clinical GVHD is thereafter tapered. Although widely accepted, this arbitrary time point for initiation of immunosuppression withdrawal may not be ideal for all subjects as some subjects may benefit from earlier withdrawal of immunosuppression to boost the anti-tumor effect of the graft. Conversely, subjects with impending GVHD may benefit from longer duration of prophylaxis.

Attempts to prevent chronic GVHD by systemic immunosuppression have been largely unsuccessful [17, 18]. There are no human studies to our knowledge that have evaluated the possibility of topical or local modalities for chronic GVHD prevention. If proven effective, topical or local therapies could be very useful for chronic GVHD prevention given their general lack of systemic side effects.

## 2.4 GVHD Therapy

### 2.4.1 Systemic immunosuppressive agents

The treatment for GVHD consists of various systemic immunosuppressive agents, most commonly systemic corticosteroids, cyclosporine, tacrolimus, mycophenolate, and sirolimus. Long-term immunosuppressive treatment for GVHD has a variety of serious side effects including life-threatening infections, aseptic bone necrosis, hypertension, and secondary diabetes [3, 19].

#### Systemic corticosteroids

Corticosteroids are currently the most commonly used systemic treatment of both acute and chronic GVHD. Although systemic corticosteroids were ineffective for prevention of GVHD and were associated with an increased number of complications like infections and aseptic bone necrosis, the preventive potential of topical therapy has not been investigated. Immunosuppressive and anti-inflammatory effects of corticosteroids are mediated through many mechanisms, including immune cell apoptosis. Corticosteroids have been shown to prevent development of dermal dendritic cells in vitro [20]. Additionally, topical corticosteroids induced apoptosis in the murine epidermal Langerhans cells [21]. The critical role of dendritic cells in the development of GVHD has been outlined in several studies. One study demonstrated the potential of GVHD prevention via depletion of host antigen presenting cells in a murine model [22]. In another animal study, local depletion of Langerhans cells in the skin prevented GVHD.

#### 2.4.2 Topical corticosteroids

Systemic treatment can be supplemented by topical administration of corticosteroids or tacrolimus. Dexamethasone is a readily available corticosteroid used topically and systemically in a wide variety of conditions. It is the only corticosteroid commercially available in the generic solution form for internal use. Dexamethasone does not cross-react in plasma cortisol assay. Dexamethasone solution or elixir is intended for systemic use, but is widely used topically by oral medicine practitioners for the treatment of oral ulcerative conditions due to convenience of administration and lack of irritation from a vehicle. Dexamethasone in the rinse form has been used for the treatment of oral manifestations of GVHD [23]. There are few side effects associated with oral topical corticosteroid use, the most common being oral candidiasis. Since most patients after stem cell transplantation receive antifungal agents preventively, the incidence of this complication is likely to be low.

Corticosteroids have been shown to possess several properties that make them attractive candidates for topical use with the goal of oral GVHD prevention. For example, they interfere with dendritic cell maturation, but not migration [24]. Keeping dendritic cells in an immature state could be advantageous in

the peripheral tissues, because the immature dendritic cells have been shown to play a key role in induction of tolerance [25]. Dexamethasone has been shown to induce immunosuppressive IL-10 producing dendritic cells which may potentially induce tolerance to peripheral tissue antigens [26].

[figure not shown]
## **2.5 Scientific and Clinical Justification**

Prevention of oral GVHD by topical agents is an attractive strategy because it would potentially avoid the adverse effects associated with systemic immunosuppression. Most importantly, using immunosuppressive and tolerizing agents locally would concentrate the effects in the area where they are beneficial, as GVHD occurs in response to recognition of peripheral antigens by activated donor T-cells. Conversely, use of systemic agents for the same purpose would interfere not only with the undesirable GVH response, but also with immune responses directed against the malignancy (i.e. the graft vs. tumor effect), which is the principal mechanism through which reduced intensity transplants achieve sustained disease remission.

There are no studies of dexamethasone absorption when used topically in the oral cavity and expectorated. The systemic effects of topically administered dexamethasone solution have not been investigated. Since this is a commonly used agent for the treatment of oral inflammatory conditions including GVHD, knowledge of the degree of systemic action would be valuable. If the absorption is significant, some degree of adrenal suppression is likely. This may have implications in many situations when systemic effects of steroids are undesirable.

We therefore propose a trial of topical dexamethasone solution for prevention of chronic oral GVHD in stem cell transplant recipients ages 12 and older. Additionally, this study will provide valuable insights into the cellular and molecular alterations associated with the development of chronic GVHD and treatment with topical corticosteroids. This will lead to better understanding of the pathogenesis of chronic GVHD and potentially development of new therapeutic interventions.

### 3. STUDY DESIGN

This is a pilot Phase II, randomized, double blind, prospective, parallel group study. Consenting subjects between 90 and 100 days post hematopoietic stem cell transplantation and without evidence of oral chronic 07-H-0005 8  
[name].  
February 3, 2021  
Amendment AA

GVHD will be randomized 50/50 to dexamethasone 0.01% or placebo oral rinse. Subjects will be evaluated at monthly intervals during the 3 months of active prophylaxis and 6 months after the intervention period is completed. Development of clinically significant oral chronic GVHD will serve as the primary endpoint and be defined in this study as objective score of 3 or higher on Lichen Planus Severity Scale (Appendix C).

## **4. ELIGIBILITY ASSESSMENT**

### **4.1 Inclusion Criteria**

- 4.1.1 History of allogeneic hematopoietic stem cell transplantation within 60-90 days of enrollment.
- 4.1.2 Age 12 or older.
- 4.1.3 Ability to rinse and expectorate study medication rather than swallow it.
- 4.1.4 Ability and willingness to come to Clinical Center for follow-up appointments and at the time of development of symptoms/signs suggestive of oral GVHD.

### **4.2 Exclusion Criteria**

- 4.2.1 Clinically significant oral chronic GVHD at the time of the screening.
- 4.2.2 Active viral or fungal infection involving oral cavity not resolving by day 90.
- 4.2.3 Platelet count < 20,000/ml at the time of the screening appointment.
- 4.2.4 Life expectancy less than 4 months at the time of enrollment.
- 4.2.5 Documented hypersensitivity to dexamethasone.
- 4.2.6 Pregnancy or lactation.
- 4.2.7 Inability to understand the investigational nature of the study.
- 4.2.8 Inability to provide informed consent.

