## **6. CLINICAL MONITORING AND ASSESSMENTS**

### **6.1 Pre-study Evaluation and Assessments**

#### **6.1.1 Eligibility assessment**

Subjects will be screened for eligibility between days 60 and 90 post transplant using the following assessments which are done under the subject's parent transplant protocol or the NHLBI screening protocol 1997-H-0041:

- Review of medical history
- Review of concomitant meds
- Blood pressure
- Complete oral examination
- Complete blood count (CBC with diff) –done concurrently with post transplant monitoring
- Consent if eligible and randomization

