#### **6.1.2 Baseline assessments**

- Serum chemistry (Acute Care (Na, K, Cl, CO2, Creatinine, Glucose, and Urea Nitrogen), Mineral (Phosphorus, Magnesium, Albumin, and Calcium), Hepatic (Alk Phosphatase, ALT, AST, Total Bilirubin, and Direct Bilirubin), and Other (Total Protein, CK, Uric Acid, and LD) panel) done concurrently with post transplant monitoring
- Pregnancy test (females of child bearing potential)
- Serum cortisol level (results blinded to investigators)
- The 0-10 Scale for Oral Pain (see Appendix A)
- The 0-10 Scale for Oral Xerostomia (see Appendix A)
- GVHD Severity Scale (see Appendix B)
- Lichen Planus (Oral GVHD) Severity Scale (see Appendix C)
- Disease specific quality of life - OHIP-14 scale (ages 18 and older only-Appendix D)
- Oral photographs (Optional)
- Oral lesion documentation
- Buccal mucosal less than approximately 6mm punch biopsy (ages 18 and older only) (optional)
- Research blood sample collection
- Research saliva sample collection
- Growth chart (length for age, weight for age percentiles and body mass index for age percentiles, pre-pubertal children) (if a hand x-ray is available on parent transplant protocol, the results will be reviewed)

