### **8.3 Primary Endpoint**

The primary objective of this study is to evaluate the safety and efficacy of topical dexamethasone 0.01% solution used as an oral rinse for prevention of oral chronic graft versus host disease. The primary endpoint is the proportion of subjects that develop clinically significant (severity score 3 or higher) oral chronic GVHD by three months post dexamethasone administration. For the purposes of this study, oral chronic GVHD with the objective score of 3 or higher on a 6-point oral GVHD scale (Appendix C) will be considered clinically significant. An intention to treat analysis will be conducted as the primary analysis.

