### **8.8.2 Principal investigator decision:**

Subjects will be taken off study during the 3 month study drug administration period:

- if they develop oral chronic GVHD in the period between baseline assessments and first dose of study drug (subjects will be reassessed between post-transplant days 90 and 100 to ensure absence of oral chronic GVHD and reinforce protocol procedures)
- if they are unable to comply with the study visits or become severely ill and cannot comply with the intervention
- if they reach the primary endpoint of clinically significant oral chronic GVHD
- if they have relapse of their underlying disease (leukemia subjects, see section 10.3.1 risk of tumor lysis)

These subjects will be asked to complete the required off study drug evaluations and end of study assessments.

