## APPENDIX C : ORAL GVHD SEVERITY SCALE

**Lichen Planus (Oral GVHD) Severity Scale** (adapted from Thongprasom K et al, 2003)

Score 5:	White striae with erosive area > 1 cm 
Score 4:	White striae with erosive area < 1 cm 
Score 3:	White striae with erythematous area > 1cm 
Score 2:	White striae with erythematous area < 1 cm 
Score 1:	Mild white striae only
Score 0:	No lesions, normal mucosa

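### Subjects with oral lesions at Appendix C score 1–2 can be randomized into a prevention trial whose primary test neither stratifies by nor names the baseline score

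*Combined protocol and SAP*

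**What the plan says.** Who may enter:

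- Section 3 describes the population at randomization as "Consenting subjects between 90 and 100 days post hematopoietic stem cell transplantation and without evidence of oral chronic" GVHD. It sets no severity threshold.
- Section 4.2.1, the only matching eligibility criterion, excludes "Clinically significant oral chronic GVHD at the time of the screening". Section 8.3 defines the term: "oral chronic GVHD with the objective score of 3 or higher on a 6-point oral GVHD scale (Appendix C) will be considered clinically significant".
- On the Appendix C scale only score 0 is free of lesions. Score 1 is "Mild white striae only". Scores 2 and 3 both add erythema and differ only in whether its area is below or above 1 cm².
- Section 6.1.1 states "Subjects will be screened for eligibility between days 60 and 90 post transplant" and lists consent and randomization within that step. Section 4.3 likewise has the pharmacy randomize once eligibility and consent are confirmed.
- Section 8.8.2 takes subjects off study "if they develop oral chronic GVHD in the period between baseline assessments and first dose of study drug". In the same bullet it plans a reassessment at days 90–100 to confirm that oral chronic GVHD is absent. Section 8.2 has subjects who leave for this reason replaced.

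How the primary endpoint is compared:

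- Section 6.1.2 collects the "Lichen Planus (Oral GVHD) Severity Scale (see Appendix C") at baseline.
- Section 4.3 stratifies randomization by conditioning type only.
- Section 8.5 analyses all randomized subjects with a continuity-corrected chi-squared test. It also promises adjustment for age and for further covariates, with systemic immunosuppression as the example, and stratified analyses for immunosuppressive agents and other prognostic factors that it does not list.

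**The concern.** The sections do not agree on who is in the trial. A subject with visible lesions at score 1 or 2 meets the listed criteria but does not fit the population that Section 3 describes, if those lesions count as evidence of oral chronic GVHD.

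The objective in Section 1.1 is prevention. For a score 2 entrant, enlargement of an existing erythematous area past 1 cm² is enough to become an event. Such events would be pooled with new onset in a mixture that the plan neither controls nor reports. Entry score plausibly predicts reaching score 3, yet with 36 per arm it is left to chance between the arms. If the rinse works less well on established lesions than on clear mucosa, the treatment difference would also be diluted.

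**Working it through.** **1. Can a score 1–2 subject reach the analysis set?**

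| Step | Rule | Score 1–2 subject |
|---|---|---|
| Screening, days 60–90 (4.2.1, 6.1.1) | Exclude score 3 or higher | Passes |
| Randomization (4.3, 6.1.1) | After eligibility and consent, listed in the screening step | Randomized |
| Randomization (Section 3) | Days 90–100, no evidence of disease | Conflicts with the rows above |
| Pre-dose check, days 90–100 (8.8.2) | Confirm absence; remove if disease developed since baseline | Lesions already present at baseline do not meet the removal wording |
| Analysis (8.5) | All randomized subjects | Included |

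On the listed criteria and the Section 6.1.1 timing, the subject is in the intention-to-treat set. On the Section 3 reading, the subject is not.

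**2. The plan's own figure.** Inputs from Section 8.2: 15% versus 45%, 36 per arm, alpha 0.05 (taken as two-sided). Pooled-variance formula without continuity correction:

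- Null standard error = √(2 × 0.30 × 0.70 / 36) = 0.108
- Alternative standard error = √[(0.15 × 0.85 + 0.45 × 0.55) / 36] = 0.102
- Power = Φ[(0.30 − 1.96 × 0.108) / 0.102] = 80.7%

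The stated 36 per arm for 80% power reproduces.

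**3. Chance imbalance (illustration).** The documents give neither the share f of score 1–2 entrants nor their risk. Assume f = 10–30% and a placebo event risk r = 70–80% among them, with overall placebo risk held at 45%.

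- SD of the between-arm difference in share = √(2f(1 − f)/36). At f = 20% this is √(0.32/36) = 9.4 points.
- Placebo risk gap g = (r − 0.45)/(1 − f). At f = 20%, g = 31.25 or 43.75 points, so the rest are at 38.75% or 36.25%.
- Shift per SD, equal absolute gap in both arms = SD × g.
- Shift per SD, proportional effect (risk ratio 0.15/0.45 = 1/3, imbalance split evenly between arms) = SD × (g + g/3)/2 = SD × 2g/3.

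| f | SD (points) | g (points) | Shift, proportional | Shift, equal gap |
|---|---|---|---|---|
| 10% | 7.1 | 27.8–38.9 | 1.3–1.8 | 2.0–2.7 |
| 20% | 9.4 | 31.3–43.8 | 2.0–2.7 | 2.9–4.1 |
| 30% | 10.8 | 35.7–50.0 | 2.6–3.6 | 3.9–5.4 |

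The yardstick is the standard error of the difference from step 2, 10.2 points. At f = 20% with an equal gap, this source makes up (2.9/10.2)² to (4.1/10.2)², or about 8–16% of the variance. That is roughly what stratification could recover.

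**4. Dilution (illustration).** Now assume that the rinse has no effect on existing lesions, that 45–70% of score 1–2 entrants reach score 3 in either arm, and that the rest keep 45% versus 15%. At f = 20% with 70% progressing:

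- Placebo = 0.8 × 0.45 + 0.2 × 0.70 = 50%
- Active = 0.8 × 0.15 + 0.2 × 0.70 = 26%

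The difference falls from 30 to 24 points. Power at 36 per arm, by the formula in step 2:

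| f | Power |
|---|---|
| 0 | 81% |
| 10% | 68–70% |
| 20% | 56–58% |
| 30% | 44–47% |

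**The case against.** The strongest defence is that there are two gates. Section 4.2.1 governs screening, while Section 3 and the reassessment in 8.8.2 govern the start of study drug at days 90–100, when absence of disease is checked. Section 7.3.3.1 fits this, since it looks for diagnostic biopsy features in subjects without clinical signs. This stands in part: some score 1–2 subjects may be caught before dosing. It does not close the gap, because the removal wording covers only disease that develops after baseline, randomization is listed at the earlier step, and biopsies are optional and limited to adults.

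Four stronger readings are tempting, and the documents do not support them.

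- *The primary test is biased or inflates type I error.* It does not. Chance imbalance under randomization is already within the standard error, and an unadjusted test in a 72-subject pilot is legitimate.
- *The plan rules out adjustment for baseline score.* Section 8.5 leaves room for unlisted covariates and prognostic factors. The accurate statement is that baseline score is not named.
- *The same score is both eligible and a ground for replacement.* Sections 8.2 and 8.8.2 give no score, and nothing makes score 1 on an adapted lichen planus scale diagnostic of oral chronic GVHD. The threshold there is undefined.
- *Progression to score 3 contradicts the endpoint.* Sections 8.1.1 and 8.3 concern clinically significant disease, so excluding only subjects already at that level is a possible design. The trouble is that Section 3 says otherwise.

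It is also fair that no document states how many score 1–2 subjects entered, or how strongly the score predicts the endpoint.

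**Conclusion.** The inconsistency is real and bears on who is analysed. As written, score 1–2 subjects can be randomized and counted, and the primary comparison takes no specified account of their baseline score.

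The effect of chance imbalance is moderate. At an assumed 20% share it is about 2–3 points per SD if the effect is proportional, or 3–4 points if the absolute risk gap is equal in both arms, against a standard error of about 10 points and a target difference of 30. Dilution could cost more power, but only if the rinse does little for existing lesions, on which the documents are silent. All of these sizes rest on assumed shares and risks. The textual conflict, and the absence of baseline score from the stratification factors and named covariates, do not.

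**What to change.** 1. Reconcile Sections 3, 4.2.1, 6.1.1, 8.2 and 8.8.2 to one stated Appendix C threshold and one time point at which it is applied relative to randomization. The choice is the investigators'.
2. Before unblinding, pre-specify the primary comparison stratified by baseline Appendix C score (0 versus 1–2) and conditioning type, for example by Mantel-Haenszel. Keep the continuity-corrected chi-squared test as a sensitivity analysis. Naming the factors now also removes the freedom that Section 8.5 leaves to choose covariates after the results are known.
3. Report events by arm and baseline score. If every entrant scored 0, the baseline table settles the matter and the stratification reduces to conditioning type.

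The cost is wording and one analysis specification; the score and the conditioning stratum are already recorded. The drawback is sparse strata. About 36 × 0.15 + 36 × 0.45 = 21.6, or 22, events are expected, and a 20% share gives about 0.2 × 72 = 14 subjects at score 1–2 across two arms and two conditioning types.
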